4.3. Data Definitions and Deviations

4.3.1. Bladder Diary Endpoints

The bladder diary records what time subjects woke up for the day, what time they went to bed, and asks the subjects to record every time they had a urination event. For each event, subjects recorded the time, if they had a need to urinate immediately, if they urinated in the toilet, if they had accidental urine leakage, and if they had leakage what the main reason was for the leakage (urge or other) for 3 days and volume voided per micturition (over one 24-hour period) prior to each study visit. If fewer than three days were collected within the diary window, the average of the days within window will be used. If more than three days were collected within the diary window, the average of the three closest days to the nominal timepoint will be used.

The following efficacy parameters will be derived based on the Diary data for baseline, Weeks 2, 4, 8, 12, 16, 20, 24, 28, 36, and 52.

4.3.1.1. Secondary Efficacy Endpoints (Bladder Diary)

Although these endpoints are automatically derived in eCRF Day 3 Bladder Diary page, the final statistical analysis will use the value derived by the biometrics team based on the algorithm described below.

CFB in average daily number of micturition episodes to Week 52

The number of micturition episodes will be defined as the number of times a subject has voided in the toilet as indicated on the Bladder Diary. Average number of micturition episodes per day at each study visit will be calculated as the total number of micturition records within the diary analysis visit windows described in Table 3 divided by non-missing diary days (diary days with at least one void reported).

CFB in average daily number of urgency episodes to Week 52

The number of urgency episodes will be defined as the number of times a patient has checked that he had “need to urinate immediately” micturition in the toilet or “urge” accident leakage as indicated on the Bladder Diary. Average daily number of urgency episodes at each study visit will be calculated as the total number of urgency episodes within the diary analysis visit windows divided by non-missing diary days.

CFB in average nightly number of nocturia episodes to Week 52

Average nightly number of nocturia episodes will be calculated in the same manner as average daily number of micturition episodes but only include episodes occurring during sleep (all episodes occurring after the time reported that a subject went to bed on the same diary day and prior to the time a subject reported getting up for the day on the subsequent diary day). If no subsequent time of awakening was filled out, all records after the time a subject went to bed on the day will be used.

[figure not shown]
CFB in average daily number of urge urinary incontinence (UUI) episodes to Week 52 for subjects with UI at study URO-901-3005 baseline

The number of UUI episodes will be defined as the number of times a subject has checked that they had "urge" as the main reason for accident leakage regardless of whether "other" is checked in addition to "urge". Average UUI episodes per day at each study visit will be calculated in the same manner as described above for the micturition endpoint. The UUI endpoint will be analyzed in the FAS-Ext-I and PPS-Ext-I population.

CFB in average volume voided per micturition to Week 52

The total volume voided will be the sum of all urinary volumes collected regardless of whether patients checked "Urinated in Toilet" or not. Average volume voided per micturition at each study visit will be calculated as the total volume voided divided by the total number of micturition episodes during non-missing diary days.

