9.2.1. Efficacy and Health Outcome Endpoints

For purposes of this study, the number of micturitions will be defined as the number of times a subject has voided in the toilet as indicated on the Bladder Diary. Average daily micturitions are calculated using the daily entries in the Bladder Diary, which is completed prior to each study visit. Average daily number of micturitions will be calculated as the total number of micturitions that occur on a Diary Day divided by the number of Diary Days in the Bladder Diary. Baseline will be the same baseline determined from the URO-901-3005 trial.

[figure not shown]
[figure not shown]
An urgency episode is defined as the “Need to Urinate Immediately” as indicated on the Bladder Diary. Average daily urgency episodes at each study visit will be calculated in the same manner as described above for the micturitions.

[figure not shown]
A UII episode is defined as having "urge" as the main reason for the leakage as indicated on the Bladder Diary, regardless of whether more than one reason for leakage in addition to “urge” is checked.

A nocturia episode is defined as waking to pass urine during the main sleep period as indicated on the Bladder diary.

Efficacy Endpoints:

- CFB at Week 52 in the average number of micturition episodes per day
- CFB at Week 52 in the average number of urgency episodes (urgency: need to urinate immediately) per day
- CFB at Week 52 in the average number of nocturia episodes per night
- CFB at Week 52 in the average number of UUI episodes per day in subjects with incontinence at Study URO-901-3005 baseline
- CFB at Week 52 in the average of IPSS Storage score (1-week recall)
- CFB at the Week 52 in the average volume voided per micturition

Other/Exploratory – Efficacy**Other/Exploratory – Quality of Life**

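### Volume voided per micturition adds up every recorded volume but divides by toilet-ticked voids only, so numerator and denominator can rest on different records

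*SAP*

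**What the plan says.** SAP 4.3.1.1 builds the endpoint in two steps.

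- **Numerator:** "The total volume voided will be the sum of all urinary volumes collected regardless of whether patients checked" the toilet box or left it blank.
- **Denominator:** the visit value is "the total volume voided divided by the total number of micturition episodes during non-missing diary days".

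Two definitions earlier in the same section settle what the denominator counts.

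- **Micturition episode:** "The number of micturition episodes will be defined as the number of times a subject has voided in the toilet". Protocol 9.2.1 agrees: "the number of micturitions will be defined as the number of times a subject has voided in the toilet as indicated on the Bladder Diary".
- **Non-missing diary day:** the micturition count is "divided by non-missing diary days (diary days with at least one void reported"), so a day qualifies without any volume.

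SAP 4.3.1 says that events are recorded "for 3 days and volume voided per micturition (over one 24-hour period) prior to each study visit". Protocol 8.2.1 lets the subject choose any one of the three diary days for volume.

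Neither document says how to treat a void without a volume. SAP 4.2.3 states that missing diary data are not explicitly imputed, because change from baseline is analysed by MMRM. SAP section 9 lists no change to this endpoint.

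**The concern.** The ratio is meant to describe volume per void, but its two parts are selected by different rules. The numerator takes a record if it has a volume. The denominator takes a record if the toilet box is ticked. They agree only when every ticked void was measured and every measured void was ticked. The SAP expects some records to break the second condition, since it gives an explicit instruction for volumes without the tick. It applies that instruction to the numerator alone.

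The MMRM does not repair this. It accommodates a visit with no value. It cannot see a volume missing inside a visit that still yields a number. By contrast, SAP 4.3.2.1 does give such a rule for the IPSS storage score, which is not calculated if an item is unanswered.

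The endpoint is one of six secondary efficacy endpoints, and adjusted means with 95% confidence intervals are reported for it. The model contains only the 52-week vibegron group. A drift in recording completeness between baseline and Week 52 would therefore not be offset by a control arm and would appear as change on treatment.

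**Working it through.** The plan gives no figure for this derivation, so there is nothing to reproduce. The check applies the SAP ratio as written to the volume-collection day alone.

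**Inputs.** The rules come from SAP 4.3.1.1. The documents give no mean volume and no mean void count. Assumed here: V = 150 mL per void, the same for every void, and 12 toilet-ticked voids on the day (range 8 to 15).

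**Formula.** Let T be the ticked voids, k the ticked voids without a volume, and u the measured voids without the tick.

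- SAP value = V × (T − k + u) / T
- Relative error = (u − k) / T
- Matched value (volumes divided by records that carry a volume) = V × (T − k + u) / (T − k + u) = V

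**Single visit, V = 150 mL.**

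| T | k | u | SAP value | Error |
|---|---|---|---|---|
| 12 | 0 | 0 | 150 mL | 0 |
| 12 | 0 | 1 | 150 × 13/12 = 162.5 mL | +8.3% |
| 12 | 1 | 0 | 150 × 11/12 = 137.5 mL | −8.3% |
| 12 | 2 | 0 | 150 × 10/12 = 125 mL | −16.7% |
| 12 | 1 | 1 | 150 × 12/12 = 150 mL | 0 |

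One discrepant record shifts the value by 1/T: 1/15 = 6.7% to 1/8 = 12.5%. The last row shows that the two errors can cancel within a visit.

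**Change from baseline.** Write e for the relative error at a visit. The error in change is V52 × e52 − V0 × e0. If e is the same at both visits, the change is only scaled by (1 + e). For example, with e = −1/12 a true +30 mL becomes 30 × 11/12 = +27.5 mL. If e differs, the distortion is larger. Take a complete baseline at 150 mL and a true 180 mL at Week 52 over 9 ticked voids. With one unmeasured, the value is 180 × 8/9 = 160 mL, a change of +10 mL against a true +30 mL.

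**How the matched ratio fares if unmeasured voids differ in size.** Take 12 voids, 10 measured at 150 mL and 2 unmeasured.

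- If the two were 200 mL, the true mean is (1500 + 400)/12 = 158.3 mL. Matched gives 150 (−5.3%); the SAP ratio gives 125 (−21.1%).
- If they were 100 mL, the true mean is (1500 + 200)/12 = 141.7 mL. Matched gives 150 (+5.9%); the SAP ratio gives 125 (−11.8%).

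**Boundary.** The denominator is also not limited to the day on which volume was collected. That is a separate fault in the same sentence. Limiting the denominator to that day would leave everything above unchanged.

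**The case against.** **The ratio may be deliberate.** Protocol 8.2.1 mentions a single 24-hour volume used to derive volume per micturition. Under that design, total output over number of voids is a natural definition, and taking all collected volumes is right for the numerator. A reader might infer that the authors plainly meant the mean of individually measured voids; this text does not allow that certainty. But Protocol 8.2.1 and SAP 4.3.1 also call for volume per micturition, and the SAP ties volumes to individual toilet ticks. Even as a 24-hour ratio, output from an unticked void is counted while the void itself is not.

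**The size is not established.** A reader might infer a known bias in the group mean, or that the sign of the result is at risk. The documents support neither. They give no rate of unticked or unmeasured voids, and the errors act in opposite directions. Reversal can be constructed: in the change example above, two of nine voids unmeasured gives 180 × 7/9 = 140 mL, a change of −10 mL. It needs a complete baseline and that much loss at Week 52; with one unmeasured void the sign holds.

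**Diary quality is supervised.** Protocol 8.2.1 requires training, real-time entry, catch-up of missed events and a daily check by the subject, and sites review each completed diary. This makes large error rates less likely. It does not correct the formula.

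**The remedy carries assumptions.** It treats unmeasured voids as similar to measured ones and counts measured voids that fall outside the toilet definition. It may also give values that differ from the parent study's, whose SAP is not available here. All of this stands and belongs in the fix.

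**Conclusion.** The mismatch is in the text, and no other provision corrects it. Whenever the numbers of unticked volumes and unmeasured ticked voids differ, the rule returns a wrong value for that man and visit, even if all voids are equal in size. On the assumed 8 to 15 ticked voids per day, each unbalanced record shifts the value by about 7 to 13%, upward for an unticked volume and downward for an unmeasured void. Change from baseline is protected only if recording completeness is the same at both visits, and even then it is scaled slightly.

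The net direction and size in the group mean are unknown. There is no formal hypothesis and efficacy is descriptive, so no error rate, power or sample size is involved. What is exposed is the set of means and confidence intervals reported for this one secondary endpoint.

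**What to change.** In SAP 4.3.1.1, define the visit value as the sum of recorded volumes divided by the number of void records that carry a recorded volume on the volume-collection day, whatever the toilet tick. Apply the rule identically at baseline and at every URO-901-3005 and URO-901-3006 visit used in the analysis. Add that if only a 24-hour total exists for a visit, it is divided by the voids recorded on that same day.

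State the assumption that unmeasured voids resemble measured ones, and that measured voids without the toilet tick are counted. Keep the present ratio, limited to the collection day, as a sensitivity analysis. This also shows how far values may depart from those reported in the parent study.

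The cost is a few lines of SAP text and a modest programming change before database lock. No new data are needed if volumes are held by void, as SAP 4.3.1 suggests. The diary form is not in the documents, so this should be confirmed first.

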8.2.1. Bladder Diaries

Bladder Diary is used by subjects to record the frequency of daily OAB symptoms including all micturitions, urgency, incontinence, nocturia, one 24-hr volume voided of urine (used to derive the volume per micturition), and main reason for incontinence, and volume voided per micturition (over one 24-hour period) by selecting the respective box for each symptom occurring during the course of a given day and night.

The Bladder Diary should be completed by the subject on 3 consecutive days within the 7 days prior to Visit 12 (Week 28), Visit 13 (Week 36) and Visit 14 (Week 52). A “Diary Day” is defined as the time between when the subject gets up for the day each morning (ie, the time the subject got up for the day yesterday to the time the subject got up for the day today; approximately a 24-hour period). Urine volume may be collected during any one (1) of the 3 Diary Days prior to the visit.

At all study visits, the site staff should inquire whether the subject had any difficulties with the diary and address any questions subjects may have. Instructions for proper completion of the diary should be re-reviewed. Subjects will be trained to enter data immediately following each event (in real time) and to input data from any “missed” events as soon as they are able. They will review and confirm that data from all events occurring within the preceding Diary Day (approximately 24 hours) have been entered at a consistent time each morning (eg, upon getting up for the day).

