4.2.4.2. Analysis Visit Windows

Analysis visit windows for both diary and non-diary efficacy data are shown in Table 3. All observations will be given an analysis visit, assigned based on relative study day from the first blinded treatment in study URO-901-3005. If multiple repeats of the same assessment are observed within an analysis window, unless the measure was intended to be averaged over replicates, the record closest to the nominal time (earlier in case of a tie) will be used for by-visit summaries. If fewer than three of the diary days are within the analysis window, only the data within the window will be used to calculate visit-level averages.

Table 3: Efficacy Analysis Visit Window Slotting

Analysis window label	Non-diary data			Diary data		
	Nominal visit	Nominal day	Visit Window	Nominal visit ^a	Nominal day	Window
Baseline	Visit 3	1	NA ^b	Run-in	-1	[-7 ^c , -1]
Week 1	Visit 4	8	[2, 11]			
Week 2	Visit 5	15	[12, 22]	Visit 4	15	[7,18]
Week 4	Visit 6	29	[23, 42]	Visit 5	29	[19, 39]
Week 8	Visit 7	57	[43, 70]	Visit 6	57	[47, 67]
Week 12	Visit 8	85	[71, 98]	Visit 7	85	[68, 102]
Week 16	Visit 9	113	[99, 126]	Visit 8	113	[103, 123]
Week 20	Visit 10	141	[127, 154]	Visit 9	141	[131, 151]
Week 24	Visit 11	169	[155, 182 ^b]	Visit 10	169	[159, 179]
Week 28	Visit 12	197	[183 ^d , 224]	Visit 11	197	[187, 207]
Week 36	Visit 13	253	[225, 308]	Visit 12	253	[243, 263]
Week 52	Visit 14	365	> Day 309	Visit 13	365	[345, 385]

a Nominal visit for diary data is the visit where the diary was dispensed.

b Must have occurred prior to the first dose administered in study URO-901-3006.

c If randomization was delayed for any reason, diaries completed within 7 days prior to the baseline visit will still be considered within the analysis window.

d Must have occurred on or after the first dose administered in study URO-901-3006.

For all non-diary safety data including safety laboratory, vital signs, and PVR volume to be summarized by visit, data records will be slotted to one of the protocol-specified visits using the following algorithm:

1. Determine relative study day and last dose day:

Relative study day will be derived as described in Section 4.3.3.

Note that the date of first double-blind dose on URO-901-3005 is Day 1 and the day before the date of double-blind first dose is Day -1. There is no Study Day 0.

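### The SAP divides one day's urine volume by the micturitions on all diary days, so volume voided per micturition comes out at about one third of its true value with a complete 3-day diary

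*SAP*

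**What the plan says.** **What is collected.** Protocol 8.2.1 has the subject record events on three consecutive days but only "one 24-hr volume voided of urine (used to derive the volume per micturition"). It adds: "Urine volume may be collected during any one (1) of the 3 Diary Days prior to the visit". SAP 4.3.1 agrees: events are recorded "for 3 days and volume voided per micturition (over one 24-hour period) prior to each study visit".

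**How the endpoint is derived.** SAP 4.3.1.1 first defines total volume as the sum of every urine volume collected, whether or not the toilet box was ticked. The average is then "calculated as the total volume voided divided by the total number of micturition episodes during non-missing diary days". The only definition of the denominator's days is earlier in the same subsection, under the micturition endpoint: "non-missing diary days (diary days with at least one void reported"). It sets no condition on volume.

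**Short and long diaries.** SAP 4.3.1 says: "If fewer than three days were collected within the diary window, the average of the days within window will be used". With more than three days, "the average of the three closest days to the nominal timepoint will be used". SAP 4.2.4.2 adds that with fewer than three days in the window, "only the data within the window will be used to calculate visit-level averages".

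**Which value is reported.** SAP 4.3.1.1 sets aside the value calculated in the eCRF and uses the SAP algorithm for the final analysis.

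**The concern.** The numerator is a one-day total by design, while the denominator counts toilet voids on every diary day with a void. I found no sentence in either document that limits the denominator to the day on which volume was measured. A program that follows the SAP exactly therefore produces a quantity that is not a volume per void.

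The rule feeds the baseline summary (SAP 5.3), the baseline covariate in the MMRM, and the least squares means and 95% confidence intervals at each time point (SAP 6.1). The dry-runs in SAP 2.2 check that programs match the plan, so a program containing this error could pass them.

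The error is also not a fixed rescaling. The divisor depends on how many diary days were kept and on how often the subject voided on the days without volume measurement. Both can differ between baseline and Week 52.

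**Working it through.** The documents give no figure for this endpoint, so there is nothing to reproduce. All mL values and void counts below are assumptions for illustration. The documents also give no rate of short diaries.

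**Formula.** Let V be the volume on the one measured day, and m1, m2, m3 the toilet voids on the three days, with day 1 the measured day.

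- SAP as written: V / (m1 + m2 + m3)
- Like for like: V / m1
- Ratio: m1 / (m1 + m2 + m3), which is 1/d for d diary days with equal counts

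**Step 1: level.** Equal counts give 1/3 = 0.333 for three days and 1/2 = 0.50 for two. If the measured day has 20% fewer or 20% more voids than each of the other two, the three-day ratio is 0.8/2.8 = 0.286 or 1.2/3.2 = 0.375. At 150 mL per void the derived value is 150/3 = 50 mL or 150/2 = 75 mL. For 100 to 200 mL and three days it is 33.3 to 66.7 mL. With one day kept, the ratio is right only if that day is the measured one.

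**Step 2: change from baseline, three days at both visits.** Assume a true rise from 150 to 170 mL (+20), with 10 voids on the measured day at both visits and on every baseline day. The baseline value is 1500/30 = 50.0. With k voids on each unmeasured Week 52 day, the Week 52 value is 1700/(10 + 2k):

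| k | Week 52 value (mL) | Derived change (mL) |
|---|---|---|
| 9 | 1700/28 = 60.7 | +10.7 |
| 10 | 1700/30 = 56.7 | +6.7 |
| 11 | 1700/32 = 53.1 | +3.1 |
| 12 | 1700/34 = 50.0 | 0.0 |
| 13 | 1700/36 = 47.2 | -2.8 |

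**Step 3: change from baseline, unequal numbers of days.** Assume equal voids per day and that the measured day is kept.

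- No true change, three days at baseline and two at Week 52: 150/2 - 150/3 = +25.0 mL. The range is +16.7 to +33.3 for 100 to 200 mL per void.
- True change of +20 mL, two days at baseline and three at Week 52: 170/3 - 150/2 = -18.3 mL. The range is -10.0 (120/3 - 100/2) to -26.7 (220/3 - 200/2).

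**Step 4: losing the measured day.** If each of the three days is equally likely to be the measured one, it is among the days kept with chance 2/3 when two remain and 1/3 when one remains. The SAP does not say what the value is when it is not.

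**Step 5: precision.** Under a uniform factor of 3 and an assumed standard error of 6 mL, an estimate of 20 (SE 6) becomes 6.7 (SE 2). The ratio of estimate to SE is 3.33 in both cases. The estimate and interval are mis-scaled, but relative precision is unchanged.

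**The case against.** **Intent.** Both documents attach a single 24-hour period to volume per micturition, so the whole ratio might be meant for one day, with non-missing meaning non-missing for volume. That may be what the sponsor intended. But the only stated definition of a non-missing day says otherwise, so a programmer who did the sensible thing would be departing from the written algorithm.

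**Windows.** For visits on schedule, windowing rarely removes the measured day. A Week 52 visit falls on Days 361 to 369 (365 ± 4), so a diary in the preceding 7 days falls on Days 354 to 368, inside the window of 345 to 385. The baseline window is the 7 days before Day 1, with a footnote covering delayed randomization. At Weeks 28 and 36 only the earliest possible day (186 or 242) falls outside. This stands: loss of the measured day mainly needs an off-schedule visit or an incomplete diary. SAP 9.3 does note that visit windows were widened during the pandemic. The main error does not depend on this, because it is present with a complete diary.

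**Sign reversals.** These are constructed cases for single subjects. Nothing here shows that a group mean would reverse. With complete diaries and similar counts the effect is close to a constant rescaling.

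**Detection.** A threefold gap from the eCRF value might well be noticed. No such comparison is required, however.

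**Consequence.** Safety is the primary objective, there are no formal hypotheses, and the other five secondary endpoints are unaffected. That limits the severity. But for a descriptive endpoint, the estimate in mL and its interval are the whole result.

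**Conclusion.** The concern holds: the derivation is wrong as written. With a complete diary it gives about one third of the true volume per void, and with two days about one half. These factors do not depend on the assumed volume or void count, only on similar voiding across the diary days. The mL illustrations and the subject-level reversals do rest on assumed values. The finding concerns the written algorithm. The actual program and the parent-study derivation are not available, so it does not claim that reported results are wrong. Because Protocol 9.4.1 makes efficacy descriptive, no error rate, power or decision changes. It should be fixed before the analysis is run.

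**What to change.** Replace the sentence in SAP 4.3.1.1 with wording such as:

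> Average volume voided per micturition is the total volume recorded on the volume-collection diary day divided by the number of micturition episodes on that same diary day. If no volume-collection day falls within the analysis window, the value is missing.

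Apply it identically at baseline and at every visit. State that the volume-collection day is used even when it is not among the three days closest to the nominal day. Also state what happens if a window holds more than one volume-collection day, or if a void on that day has no recorded volume.

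Check the result against the parent-study derivation and the eCRF value. Protocol 9.4.1 takes baseline from the parent study, so any difference from that study's derived baseline needs to be resolved and documented.

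A separate, optional point is that the numerator includes volumes not marked as toilet voids while the denominator counts toilet voids only, a smaller upward mismatch. If the sponsor aligns the two, record it as a change in SAP Section 9.

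The cost is one SAP sentence with the short clarifications above, the derivation code for baseline and all visits, and the cross-check. No new data and no protocol amendment are needed.
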